10.2 Operational definitions for AEs/SAEs

We will follow WCTU's SOP on 'Safety Reporting' for all Adverse Events (AE) and Serious Adverse Events (SAE).

Exemptions from AE/SAE reporting

The following events listed in Table 9 will not be reported as AEs or SAEs (if hospitalisation is required) as they will be reported and recorded as part of trial efficacy outcomes and are common AEs/SAEs in this population. Comparative rates of these events will be monitored by the DMC:

Condition	
Admission to hospital for miscarriage (<24 weeks)	
Admission to hospital for stillbirth (≥24 weeks)	
Admission to hospital for a molar pregnancy	
Admission to hospital for an ectopic pregnancy	
Fetal growth problems / admission to hospital for fetal growth problems	
Admission to hospital for unstable lie	
Admission to hospital for delivery	
Admission to hospital for delayed delivery	
Admission to hospital for threatened pre-term labour	
Admission to hospital for pre-term birth	
Admission to hospital for Caesarean section	
Congenital abnormality or birth defect	

Table 9 – Events collected via CRF exempt from AE/SAE reporting

If treatment or intervention is required following a medical complication that fulfils the criteria for a SAE i.e. is life-threatening or prolongs hospitalisation for any of the events listed in Table 9 then a SAE should be reported. For any of the events listed in Table 9 prolonged hospitalisation is defined by the following:

- ≥4 days for a pregnancy <24 weeks
- \geq 7 days for a pregnancy \geq 24 weeks

In addition some events that would meet a definition of a serious adverse event; for example admission to hospital due to nausea and vomiting, headaches or vaginal bleeding are relatively common in pregnancy. SAEs that **do not** require time critical reporting but should be reported as AEs on the Adverse Event Form are listed in Table 10:

Table 10 – Adverse Events exempt from SAE reporting but still recorded as AEs

Condition	
Admission to hospital for nausea and vomiting	
Admission to hospital for headaches	
Admission to hospital for raised blood pressure	
Admission to hospital for urinary tract infection	
Admission to hospital for vaginal bleeding	
Admission to hospital for pregnancy induced hypertension	

10.3 Recording and reporting of AEs SAEs, SARs AND SUSARs

AEs and SAEs will be collected from the time of written consent for randomisation until 30 days post last trial treatment (last capsule taken). AEs and SAEs will not be collected for participants who do not have CE.

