Smoking history		•								
Medical History		•								
Concomitant medication review		•		•						
Obstetric History		•								
Pregnancy History		•								
Review Eligibility		•		•						
Pregnancy Test		•		•	3					
Contraception use review		•		•	•					
Period Review		•		•	• 3					
Written Consent Screening CERM A or CERM B ³		•								
Registration		•								
Endometrial Biopsy			•		3					
Swabs – CERM B Only ³			3		• 3					
Inform patient of CE results			•							
Adverse event review				•	•	•				1
Written Consent Randomisation ²				•						
Randomisation				•						
Treatment instructions				•						
Dispense medication				•						

The CERM trial Protocol

Treatment compliance check			•					
Contact patient every 3 months to determine pregnancy				•				
Pregnancy confirmation					•	• 4		
Ultrasound					•	•	6 5	
Concomitant medication review (on trial)			•		•	•	•	•
Pregnancy complications ⁴					•	•	•	•
Pregnancy outcome assessments								•

¹Verbal consent must be given (and documented) prior to biopsy kits being given/sent

²Written informed consent must be given prior to any trial specific procedures taking place.

³CERM B patients only (UHCW ONLY)

⁴ If appropriate

⁵Only if clinically indicated

⁶Timing of visit as per local hospital policy

Table 6 – Trial tasks and Milestones

Tasks	Time period (months)
Trial preparation: approvals (ethics, R&D), research governance (oversight committees (TMG, TSC and	⁻ 2 - ⁻ 1 (pre-start)
DMC), staff training), develop project management plan, registration, contracting, new appointments,	
send capacity and capability questionnaires to trial sites, trial administration processes (participant files,	
master file), trial branding, and social media.	
Trial set-up: liaise with trial pilot sites, track R&D, develop randomisation service, develop data collection	1 - 3
process, prepare training manual, print recruitment information (introduction letter, participant	
information sheet, participant information leaflet, posters) and prepare site-initiation materials.	
Site set-up: Initially ten sites; four per month (not including the first and last months, August and	4 - 22
December).	
Participant recruitment: n=1,500 randomised	5 -30
Feasibility: after six months when >68 participants have been recruited.	Around 10
Follow-up: birth.	7 - 38
Interim analysis: when data on primary outcome on n=250, 500, 750, 1,000 available.	Around 9-21
Data analysis	36 - 40

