10.3.1 Recording of Adverse Events

All AEs (except those specified in table 9) that occur in either the participant, fetus or infant should be recorded on an Adverse Event Form and in the participants' medical notes.

If the AE is ongoing at the time of reporting then any change to the condition or outcome of the event should be reported on an Adverse Event Follow-up Form.

30 days after the participant has completed their treatment there is no requirement for the hospital research team to identify any new AEs. However, if the hospital research team become aware of an SAE that has occurred post 30 days since last treatment received and the Investigator considers the SAE to be related to doxycycline/placebo, then the Investigator should report the SAE.

Adverse Event data will be reviewed by the CERM TMG and by the DMC.

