10.3.2 Reporting SAEs and SUSARs

All SAEs/SUSARs that occur in the woman, fetus or infant must be recorded on the Serious Adverse Event Form and emailed:**[contact]** or faxed: **[name]** to the WCTU **within 24 hours** of the research staff becoming aware of the event. Once all resulting queries have been resolved, WCTU will request the original form be posted to the WCTU and a copy to be retained on site. For each **SAE/SUSAR** the following information will be collected:

- full details in medical terms and case description
- event duration (start and end dates, if applicable)
- outcome
- severity assessment
- causality (relatedness to trial drug), in the opinion of the investigator
- whether the event would be considered expected.

Any change of condition or other follow-up information should be emailed/faxed to WCTU on the Serious Adverse Event Follow-Up form as soon as it is available or at least within 24 hours of the information becoming available. Events will be followed up until the event has resolved or a final outcome has been reached.

The causality of SAEs (i.e. relationship to trial treatment) will be assessed by the investigator(s) on the SAE form.

Relationship to trial medication	Description
Unrelated	There is no evidence of any causal relationship
Unlikely to be related	There is little evidence to suggest there is a causal relationship (e.g. the event did not occur within a reasonable time after administration of the trial medication or device). There is another reasonable explanation for the event (e.g. the participant's clinical condition, other concomitant treatment).
Possible relationship*	There is some evidence to suggest a causal relationship (e.g. because the event occurs within a reasonable time after administration of the trial medication or device). However, the influence of other factors may have contributed to the event (e.g. the participant's clinical condition, other concomitant treatments).
Probable relationship*	There is evidence to suggest a causal relationship and the influence of other factors is unlikely.
Definitely related*	There is clear evidence to suggest a causal relationship and other possible contributing factors can be ruled out.

Table 11 – SAE Causal relationship

If there is a possible, probable or definite relationship to the intervention, then an assessment of expectedness must also be completed by the investigator(s) on the SAE form.

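### Routine AE/SAE collection closes about day 44, yet other rules cover 24-week pregnancies and infants, and congenital anomaly is not named after birth

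*Protocol*

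**What the plan says.** - **Window.** Protocol 10.3 collects AEs and SAEs from written RCT consent "until 30 days post last trial treatment (last capsule taken". After that, 10.3.1 says "there is no requirement for the hospital research team to identify any new AEs". One late duty remains: an SAE that the site learns of and the investigator considers related must still be reported.
- **Stay thresholds.** Section 10.2 exempts the Table 9 pregnancy events from AE/SAE reporting, but requires an SAE report when a medical complication needing treatment threatens life or lengthens the hospital stay. It continues: "For any of the events listed in Table 9 prolonged hospitalisation is defined by the following". The limits are 4 days or more below 24 weeks and 7 days or more from 24 weeks. It sets no relatedness condition.
- **Infants.** Section 10.3.1 covers AEs "that occur in either the participant, fetus or infant should be recorded on an Adverse Event Form", and 10.3.2 says "All SAEs/SUSARs that occur in the woman, fetus or infant must be recorded on the Serious Adverse Event Form".
- **Follow-up checks.** Section 10.4 makes the principal investigator responsible for checking for AEs when participants are reached at follow-up. Table 5 marks AE review at the Pregnancy Review.
- **Congenital abnormality.** It is an SAE by definition in 10.1. Table 9 exempts it with the other listed events because "they will be reported and recorded as part of trial efficacy outcomes", and 10.2 adds: "Comparative rates of these events will be monitored by the DMC". It is named at the 12-week (9.6) and 20-24 week (9.7) assessments. It is not named at 9.9, nor in any outcome in section 3.

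**The concern.** The stay threshold at 24 weeks and the infant rules describe events that cannot happen while collection is open. A site that learns of a seven-day stay after a complication at 30 weeks finds 10.2 telling it to report, while 10.3 and 10.3.1 require a report only if the event is judged related. Sites may settle this differently, and SAE counts would then differ for reasons unrelated to treatment.

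Section 2.3.1 records that the product characteristics contraindicate doxycycline in pregnancy, and it foresees conception in the treatment month. Those few pregnancies are where fetal and infant safety data matter most. Congenital anomaly is the outcome of greatest interest in them, and no scheduled assessment after birth names it.

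**Working it through.** There is no stated figure to reproduce; the check is calendar arithmetic plus a comparison of the rules.

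**Inputs.** Capsules for 14 days from cycle day 1 (8.6.1); 30 days after the last capsule (10.3); condoms for the whole treatment cycle (7.7); cycles of 21 days or less and 42 days or more excluded (6.2), so cycle length L runs from 22 to 41 days; half-life 16-22 hours (2.3.1); completion call within 6 weeks of randomisation (9.4), then contact every 3 months (9.5.2).

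**Assumptions.** Ovulation falls 14 days before the next period; 3 months is 91 days; the completion call is made on or after day 14.

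**1. Window.** Day 1 is the first capsule. Closure is 14 + 30 = day 44.

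**2. When 24 weeks (168 days) is reached.** Results for L = 22, 28 and 41:

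| Conception | Dated from | Day of 24 weeks | Days after closure |
|---|---|---|---|
| Treatment cycle | last period: 1 + 168 | 169 for any L | 125 |
| Treatment cycle | ovulation: (L - 14) + 154 | 162, 168, 181 | 118, 124, 137 |
| First permitted cycle | last period: (L + 1) + 168 | 191, 197, 210 | 147, 153, 166 |
| First permitted cycle | ovulation: (2L - 14) + 154 | 184, 196, 222 | 140, 152, 178 |

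The smallest gap is 118 days. Gestation at closure, dated from the last period, is at most 43 days (6.1 weeks), so no infant exists inside the window either.

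**3. Can any pregnancy be recognised inside the window?** After conception in the treatment cycle, the next period is due on day L + 1, which is day 23 to 42 and inside the window. After conception in the first permitted cycle it is due on day 2L + 1, which is day 45 to 83 and outside. So only treatment-cycle conceptions would normally be recognised before closure.

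**4. Scheduled contacts.** The completion call falls between day 14 and day 43 (randomisation on day 1 plus 42 days). The first 3-monthly contact is then day 14 + 91 = 105 to day 43 + 91 = 134, which is 61 to 90 days after closure.

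**5. Drug exposure.** Treatment-cycle conception falls on day L - 14 = 8, 14 or 27: six days before the last capsule, on the same day, or 13 days after it. The earliest permitted conception is day 2L - 14 = 30, 42 or 68, which is 16, 28 or 54 days after the last capsule. Sixteen days is 384 hours: 384/22 = 17.5 to 384/16 = 24 half-lives. Exposure is therefore plausible only for the first group.

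**6. Congenital abnormality, section by section.** It is an SAE in 10.1; exempt in Table 9 as an efficacy outcome; absent from 3.1 to 3.3; named in 9.6 and 9.7. At 9.9, the only scheduled assessment after birth, the items are a general pregnancy-outcome entry, medication, complications, and maternal and infant infections. The comparison of rates promised in 10.2 rests, for anomalies first seen at birth, on that general entry.

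**The case against.** The case for leaving the text alone has real substance, and it rules out several stronger readings that a reader might infer.

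- **That late reporting is purely passive.** It is not. Section 10.4 has the investigator check for AEs at follow-up contacts, and randomised women are contacted every 3 months, at 12 and 20-24 weeks, and 6-8 weeks after a delivery beyond 24 weeks. A causal relationship rated only as possible already counts (Table 11). This narrows the gap, but 10.4 itself sits awkwardly with 10.3.1, which removes the duty to look for new AEs.
- **That the Pregnancy Review mark in Table 5 can never operate.** Sections 7.7 and 9.5 tell women to test when a period is late and to contact the site at once. Step 3 puts that on day 23 to 42 for a treatment-cycle conception, inside the window and for exactly the exposed pregnancies.
- **That anomalies found at birth are lost.** Table 9's title presents its entries as collected on the case report form, and the DMC is to compare them. The form is not shown and may hold the field, so a shortfall is a risk and not a certainty.
- **That the 24-week threshold is redundant and should go.** The late route for related SAEs still needs a definition of a prolonged stay.

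It can also be argued that 10.2 defines what counts as an SAE while 10.3 sets when events are collected, so nothing clashes. That would hold if 10.2 were limited to related events after the window, but it is worded as a duty to report without that limit. The look-back period of the completion call, and whether the unrestricted reporting of deaths in 10.5 extends to infants, are details that the safety procedures can settle.

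**Conclusion.** The point holds, at minor severity. The 24-week and infant rules cannot operate inside a window that closes on day 44; the shortest gap to 24 weeks is 118 days on ovulation dating, or 125 days from the last period. Sites therefore have conflicting instructions on unrelated late events. Separately, the reason given for exempting congenital abnormality does not match section 3, and 9.9 omits it by name, so the DMC comparison may be incomplete for anomalies first recognised at birth.

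The day counts rest on the 14-day luteal assumption where ovulation dating is used; the conclusion does not depend on which dating is chosen. The documents do not support the inference that the 30-day window is wrong in itself: for women who follow the contraception advice, exposure at conception is negligible and a 30-day maternal window is proportionate. The primary analysis and the sample size are unaffected.

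**What to change.** 1. Keep the 30-day window for maternal AEs and SAEs. State in 10.2 and 10.4 that after it the stay thresholds apply only to SAEs judged related under 10.3.1, and keep the 24-week threshold for that purpose.
2. As an exception, for pregnancies conceived in the treatment cycle, collect fetal and infant SAEs with a causality assessment up to the existing 6-8 week contact.
3. Name congenital anomaly detected at birth in 9.9, list it as a safety outcome in section 3 in place of the efficacy rationale behind Table 9, and report it by arm.

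The cost is a protocol amendment, one extra item at a contact that already asks about infant infections, and a few more SAE forms for the small number of treatment-cycle conceptions.

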10.3.1 Recording of Adverse Events

All AEs (except those specified in table 9) that occur in either the participant, fetus or infant should be recorded on an Adverse Event Form and in the participants' medical notes.

If the AE is ongoing at the time of reporting then any change to the condition or outcome of the event should be reported on an Adverse Event Follow-up Form.

30 days after the participant has completed their treatment there is no requirement for the hospital research team to identify any new AEs. However, if the hospital research team become aware of an SAE that has occurred post 30 days since last treatment received and the Investigator considers the SAE to be related to doxycycline/placebo, then the Investigator should report the SAE.

Adverse Event data will be reviewed by the CERM TMG and by the DMC.

10.3.2 Reporting SAEs and SUSARs

All SAEs/SUSARs that occur in the woman, fetus or infant must be recorded on the Serious Adverse Event Form and emailed:**[contact]** or faxed: **[name]** to the WCTU **within 24 hours** of the research staff becoming aware of the event. Once all resulting queries have been resolved, WCTU will request the original form be posted to the WCTU and a copy to be retained on site. For each **SAE/SUSAR** the following information will be collected:

- full details in medical terms and case description
- event duration (start and end dates, if applicable)
- outcome
- severity assessment
- causality (relatedness to trial drug), in the opinion of the investigator
- whether the event would be considered expected.

Any change of condition or other follow-up information should be emailed/faxed to WCTU on the Serious Adverse Event Follow-Up form as soon as it is available or at least within 24 hours of the information becoming available. Events will be followed up until the event has resolved or a final outcome has been reached.

The causality of SAEs (i.e. relationship to trial treatment) will be assessed by the investigator(s) on the SAE form.

Relationship to trial medication	Description
Unrelated	There is no evidence of any causal relationship
Unlikely to be related	There is little evidence to suggest there is a causal relationship (e.g. the event did not occur within a reasonable time after administration of the trial medication or device). There is another reasonable explanation for the event (e.g. the participant's clinical condition, other concomitant treatment).
Possible relationship*	There is some evidence to suggest a causal relationship (e.g. because the event occurs within a reasonable time after administration of the trial medication or device). However, the influence of other factors may have contributed to the event (e.g. the participant's clinical condition, other concomitant treatments).
Probable relationship*	There is evidence to suggest a causal relationship and the influence of other factors is unlikely.
Definitely related*	There is clear evidence to suggest a causal relationship and other possible contributing factors can be ruled out.

Table 11 – SAE Causal relationship

If there is a possible, probable or definite relationship to the intervention, then an assessment of expectedness must also be completed by the investigator(s) on the SAE form.

Section 4.8 of the SmPC relevant to the doxycycline/placebo will be used to assess expectedness of events. Up to date versions of the relevant SmPC will be monitored by WCTU

CERM Trial Team. Any updated SmPC will be sent to the MHRA for approval prior to use in the trial.

Causality and expectedness must be assessed by a clinical member of staff at the recruiting site who has been delegated this responsibility on the trial delegation log.

The CI or delegate will also review the SAE report to assess causality and expectedness. The CI or delegate will have the discretion to upgrade any events that require escalation, but will not be able to downgrade any clinical opinion made at site.

All SAEs assigned by the CI or delegate as both suspected to be related to IMP treatment and unexpected will be classified as SUSARs and will be subject to expedited reporting to the Medicines and Healthcare Products Regulatory Agency (MHRA).

SAE's deemed to be SUSARs will be reported to the REC/MHRA within the specified timelines according to UK legislation (i.e. 7 days for fatal/life threatening events and 15 days for other 'serious' categories).

WCTU will inform the Sponsor, MHRA and the REC of SUSARs within the required expedited reporting timescales.

The trial manager will liaise with the investigator to compile all the necessary information. Warwick CTU is responsible for reporting serious adverse events to the Sponsor, REC and MHRA within required timelines.

Participants are followed up throughout their pregnancy. Details of the trial follow-up duration are given in the CERM Trial summary table 5.

10.4 Responsibilities Principal Investigator (PI):

Checking for AEs and ARs when participants attend for treatment / contacted for follow-up.

- 1. Using medical judgement in assigning causality and assessing severity. Grading each adverse event using CTCAE.
- 2. Assessing expectedness using the Reference Safety Information approved for the trial.
- 3. Ensuring that all SAEs are recorded and reported to the sponsor within 24 hours of becoming aware of the event and provide further follow-up information as soon as available. Ensuring that SAEs are chased with WCTU if a record of receipt is not received within 2 working days of initial reporting.
- 4. Ensuring that AEs and ARs are recorded and reported to the sponsor in line with the requirements of the protocol.

Chief Investigator (CI) / delegate or independent clinical reviewer:

- 1. Clinical oversight of the safety of patients participating in the trial, including an ongoing review of the risk / benefit.
- 2. Using medical judgement in assigning the SAEs seriousness and causality.

- 3. If related, assessing whether and event/reaction was expected in line with the Reference Safety Information
- 4. Immediate review of all SUSARs.
- 5. Review of specific SAEs and SARs in accordance with the trial risk assessment and protocol as detailed in the Trial Monitoring Plan.
- 6. Preparing the clinical sections and final sign off of the Development Safety Update Report (DSUR).

WCTU:

- 1. Central data collection and verification of AEs, ARs, SAEs, SARs and SUSARs according to the trial protocol onto a database.
- 2. Reporting safety information to the CI, delegate or independent clinical reviewer for the ongoing assessment of the risk / benefit according to the Trial Monitoring Plan.
- 3. Reporting safety information to the independent oversight committees identified for the trial (Data Monitoring Committee (DMC) and / or Trial Steering Committee (TSC)) according to the Trial Monitoring Plan.
- 4. Expedited reporting of SUSARs to the Competent Authority (MHRA in UK) and REC within required timelines.
- 5. Notifying Investigators of SUSARs that occur within the trial.
- 6. The unblinding of a participant for the purpose of expedited SUSAR reporting.
- 7. Checking for (bi-annually) and notifying PIs of updates to the Reference Safety Information for the trial.
- 8. Preparing standard tables and other relevant information for the DSUR in collaboration with the CI and ensuring timely submission to the MHRA and REC.

Trial Steering Committee (TSC):

In accordance with the trial TSC charter, periodically reviewing safety data and liaising with the DMC regarding safety issues.

Data Monitoring Committee (DMC):

In accordance with the trial DMC charter, periodically reviewing overall safety data to determine patterns and trends of events, or to identify safety issues, which would not be apparent on an individual case basis.

